9.9.3 Data Collection Schedule

HRV data and/or blood samples will be collected at clinically relevant and study specific time intervals where possible (**Table 6**). When not possible, HRV and/or blood sample data collection will be scheduled at the patient's convenience, and/or during the next scheduled clinical lab draw. .

Table 6. Biological data collection schedule

Time Point	T1 (Baseline)	T2 (PRISM session #1 OR 1 week post enrollment)	T3 1 month (survey timepoint)	T4 3 months (survey timepoint)	T5 6 months (survey timepoint)
24-hour HRV Recording	X	X	X	X	X
Blood Sample	X		X	X	

10.0 Data and Specimen Banking

10.1 Data storage

All pharmaco-adherence, medical record, health care utilization, HRV, blood samples, RPCA survey data, and audio transcriptions will be coded and labeled with study identification numbers. All will be stored in original (hard copy) forms in locked cabinets (where relevant) and/or password-protected secure databases (for all electronic survey data) at Seattle Children's Research Institute. Upon completion of data collection, SCH will transfer the limited dataset to DFCI per the Data Transfer Agreement. Original surveys will be saved at SCH for 10 years or until final analyses are completed, whichever occurs last, in order to ensure data quality. Coded electronically saved study data will be banked indefinitely for future use by the group of investigators conducting the study and access will be controlled by the PI's. PIs will verify that additional analyses have IRB approval. Only study staff with human subjects training will have access, subject to approval by the SCH site PI, [name]. No data will be withdrawn

from the study database. Results of initial analyses will be shared with participants if participants request on the consent form that they would like a summary of study results.

10.2 Data and/or Sample Sharing

Data will not be shared outside the group of investigators conducting the study but will be fully shared during and after the study with investigators in the group. When other investigators are interested in new analyses, the PIs will verify they have IRB approval to conduct additional analyses. Coded study data will be banked indefinitely for future use by the group of investigators conducting the study and access will be controlled by the PI's. Future studies will formally test the dissemination and implementation potential of the intervention once its efficacy is confirmed. Should the intervention be effective, the intervention will be made publicly available for use by the broader medical communities caring for AYAs with serious illnesses.

11.0 Data Analysis/Management

11.1 Overview

The primary statistical analyses will be intention-to-treat to avoid confounding by non-random participant attrition or crossover. Demographics, clinical characteristics, items within the RPCA, adherence data, and costing data will all be summarized at each time-point using descriptive statistics: frequencies and proportions for categorical variables, means and standard deviations for continuous variables, or median and interquartile range if distribution is skewed. All analyses will be adjusted for patient age and site, as randomization is stratified by age and site, as well as baseline characteristics clearly imbalanced between groups. Additional baseline characteristics we consider as potential confounders include sex, race, and primary language spoken at home.

11.2 Sample Size Determination and Power

Our focus for sample size estimation is the primary outcome (Aim 1): mean HADS scores at 6-month observation. In the following table we list minimum clinically important differences (MCID) for various outcomes and detectable differences (DD) with our proposed sample size. Sample size is based on preliminary data from our Phase II RCT suggesting AYA HADS scores are normally distributed with mean score of 11.1 (SD=6.2). Assuming 20% attrition, we will randomize 90 AYAs (45 per arm) to obtain an evaluable sample size of 70 AYA participants (35 per arm). This sample size achieves 80% power to detect a 4.2-point increase in the mean 6-month total HADS score. This means 35 per arm will provide us >80% power to detect MCID 3.1 in the primary outcome HADS. Detectable differences for secondary patient- and parent-reported outcomes given this sample size are shown in **Table 7**. Sample size calculations have limited roles in economic analyses due to wide variability in distribution of costs and corresponding to infeasibly large requirements based on traditional inference.^{121,122} Economists therefore focus on determining cost-effectiveness, as described above, including confidence intervals to reflect the precision of estimates.

Table 7. Detectable Differences between groups (in primary and secondary aims including patient- or parent-reported outcomes measures) given 80% power and 5% Type I error rate

Aim	Outcome (Instrument)	Population norms	Source	MCID	DD (SD)
1	AYA Anxiety/Depression (HADS total)	Mean 11.1 (SD 6.2)	Phase II RCT	3.1	4.2 (6.2)
2A	AYA Symptom Burden (MSAS)	Mdn 8.5 (IQR 4.3-14.0)	Published Data ⁹⁸	(not published)	4.9 (7.2)
	AYA Quality of Life – General (PedsQL 4.0)	Mean 70.9 (SD 17.2)	Published Data ¹²³	4.4	11.7 (17.2)
	AYA Quality of Life – Cancer Specific	Mean 65.3 (SD 16.3)	Phase II RCT	(not published)	11.1 (16.3)
	AYA Hope (Hope Scale)	Mean 49.6 (SD 8.3)	Phase II RCT	(not published)	5.6 (8.3)
2D	Anxiety (GAD-7)	2.95 (SD 3.4)	Published Data ⁹	(not published)	2.3 (3.4)
	Depression (PHQ-8)	3.3 (SD 3.7)	Published Data ¹⁰	5.0	2.5 (3.7)
	Parent physical quality of life (SF-36 PCS)	Mean 50.3 (6.9)	Published Data ¹²⁴	3-5	4.7 (6.9)
	Parent mental quality of life (SF-36 MCS)	Mean 42.9 (11.9)	Published Data ¹²⁴	3-5	8.1 (11.9)

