11.4 Analysis Plan

11.4.1 Primary Outcome (Anxiety and Depression [HADS scores]). Our primary outcome is AYA reported total HADS score at 6 months. Because the amount of change depends strongly on the initial score at baseline we will control for baseline score as a covariate in the regression. Regression models will be used to estimate mean-level differences and 95% confidence intervals comparing scores in the PRISM intervention to those in usual care. The total HADS score will be the outcome, and PRISM intervention indicator will be the predictor of interest. Baseline HADS score, age group, site and other unbalanced confounders will be covariates in the regression. With this model specification, the regression coefficient of PRISM indicator captures the difference in the average changes (from baseline to 6 months) for the HADS score between PRISM arm and usual care arm. Thus the primary hypothesis can be tested by applying the Wald t-test to the regression coefficient of PRISM indicator. The same analysis will be undertaken for the domain subscales of anxiety and depression (HADS-A and HADS-D subscale scores).

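### The claim of more than 80% power for the HADS MCID of 3.1 is wrong: section 11.2's own inputs give about 54%

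*Combined protocol and SAP*

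**What the plan says.** Section 11.2 (Sample Size Determination and Power) bases the sample size on mean total HADS at 6 months, with a mean of 11.1 and an SD of 6.2 from the phase II trial. It plans to randomize 90 patients, allows 20% attrition and expects 70 evaluable, 35 per arm.

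For these inputs it puts the difference detectable with 80% power at 4.2 points on total HADS. The sentence that follows draws a conclusion for the MCID: "This means 35 per arm will provide us >80% power to detect MCID 3.1 in the primary outcome HADS".

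Table 7 in the same section, calculated "given 80% power and 5% Type I error rate", lists HADS total with an MCID of 3.1 beside a detectable difference of 4.2.

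Section 11.4.1 (Primary Outcome) describes the analysis. On baseline HADS it says "we will control for baseline score as a covariate in the regression", and age group and site are also in the model. On estimation, the plan is for mean differences between the arms with 95% confidence intervals. No baseline to 6-month correlation or residual SD appears anywhere in the document.

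**The concern.** The second power sentence is presented as a consequence of the first, but the inference runs backwards. If 4.2 points is what 35 per arm can detect with 80% power, then 3.1 points must have less than 80% on the same sample size, SD and alpha. Table 7 shows the same shortfall, because the detectable difference is larger than the MCID.

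This is the only place where the plan states power against the MCID for its primary outcome. A reader who relies on it would believe that a true 3.1-point benefit has less than a 20% chance of being missed. That reader would also give a null result more weight, as evidence against a clinically important benefit, than the design supports.

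**Working it through.** **Inputs.** From section 11.2: SD 6.2, 35 evaluable per arm, alpha 0.05, MCID 3.1, stated detectable difference 4.2. Sidedness is not stated, so it is tested in step 1. The method is a two-sample t-test with noncentral t and 68 degrees of freedom.

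**1. Reproduce the plan's own figures.**

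Standard error of the difference = 6.2 × √(2/35) = 1.482.

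- At 4.2, the noncentrality is 4.2/1.482 = 2.83 and two-sided power is 79.8% (80.9% by the normal approximation).
- The two-sided detectable difference at 80% power is 0.67935 × SD = 4.21 (4.15 by the normal approximation).
- The same multiplier, applied to the raw SDs, gives every row of Table 7:

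| Outcome | SD | Computed | Stated |
|---|---|---|---|
| HADS total | 6.2 | 4.21 | 4.2 |
| MSAS | 7.2 | 4.89 | 4.9 |
| PedsQL generic | 17.2 | 11.68 | 11.7 |
| PedsQL cancer | 16.3 | 11.07 | 11.1 |
| Hope | 8.3 | 5.64 | 5.6 |
| GAD-7 | 3.4 | 2.31 | 2.3 |
| PHQ-8 | 3.7 | 2.51 | 2.5 |
| SF-36 PCS | 6.9 | 4.69 | 4.7 |
| SF-36 MCS | 11.9 | 8.08 | 8.1 |

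A one-sided test would give 0.6004 × 6.2 = 3.72 for HADS, not 4.2. The section therefore used a two-sided, unadjusted calculation.

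**2. Power at the MCID on the same inputs.**

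Standardized difference = 3.1/6.2 = 0.5; noncentrality = 3.1/1.482 = 2.09.

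| Scenario (unadjusted) | Power at 3.1 |
|---|---|
| 35 per arm, two-sided | 54.1% (normal approximation 55.2%) |
| 36 per arm (90 × 0.8 = 72), two-sided | 55.3% |
| 45 per arm (no attrition), two-sided | 65.0% |
| 35 per arm, one-sided | 66.5% |
| 45 per arm, one-sided | 76.1% |

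None of these reaches 80%. Two-sided 80% at 3.1 needs either 64 evaluable per arm (128 in total, or 128/0.8 = 160 randomized), or an SD of 3.1/0.67935 = 4.56 instead of 6.2.

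**3. Credit for baseline adjustment.** The residual SD is 6.2 × √(1 − r²), where r is the baseline to 6-month correlation. All values of r are assumptions.

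| r (assumed) | Power at 3.1, 35 per arm | Detectable difference at 80% |
|---|---|---|
| 0.3 | 58% | 4.02 |
| 0.5 | 66% | 3.65 |
| 0.6 | 73% | 3.37 |
| 0.68 | 80% | 3.1 |

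The threshold follows from √(1 − r²) = 4.56/6.2 = 0.736, so r is about 0.68. Spending further degrees of freedom on age group and site changes each power by less than 0.001.

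**4. What this means for a null result.** The expected 95% CI half-width is 1.995 × 1.482 = 2.96 points unadjusted, and 2.56 at r = 0.5. A non-significant result would exclude a 3.1-point benefit only if the estimated benefit were below 3.1 − 2.96 = 0.14 points (0.54 at r = 0.5).

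**The case against.** The strongest defence is that the primary analysis is not the unadjusted t-test. Section 11.4.1 adjusts for baseline HADS and says that change depends strongly on the baseline score, so real power at 3.1 will be above 54% and could exceed 80%. That is true as far as it goes. But section 11.2 derives its claim from the 4.2 figure, which uses the raw SD, and no correlation is given to support anything better. Adjustment could make the number come true; it does not support the sentence as written.

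Three smaller points:

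- **The threshold of 0.68 is approximate and depends on n.** Allowing for chance imbalance in baseline HADS lowers power at r = 0.5 to 65.6% and moves the threshold to about 0.683. With all 45 per arm evaluable, the threshold would be about 0.55. Neither rescues a sentence that specifies 35 per arm.
- **The 4.2 figure is disclosed.** It stands in the preceding sentence and in Table 7, so a careful reader can see the shortfall, and the sample size, model and test are unaffected. This limits the damage but leaves a false statement about the primary outcome.
- **A non-significant result never by itself rules out an important benefit, even at 80% power.** This is correct. Interpretation rests on the confidence interval, which is already planned. The wrong power figure matters because it invites more confidence in a null result than the trial can give.

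It is also fair that a correlation of 0.5 is not a figure from the documents. Any adjusted power in the corrected text must be labelled as conditional on its assumption.

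**Conclusion.** The concern holds. The statement of more than 80% power at 3.1 contradicts the sentence before it and Table 7, and no reading of the stated inputs reproduces it. With 35 per arm, SD 6.2 and a two-sided 5% test, unadjusted power is about 54%. A true 3.1-point benefit would therefore be missed about 46% of the time, not under 20%. With baseline adjustment the miss rate would be about 34% at an assumed correlation of 0.5, and would fall to 20% only at about 0.68.

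The two-sided reading is inferred, but firmly, because it alone reproduces the detectable differences. The conclusion does not depend on it, since a one-sided test gives 66%. Whether the adjusted analysis reaches 80% cannot be determined from the documents.

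**What to change.** **Required.** Replace the sentence in section 11.2 with text to this effect:

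> With 35 per arm, the trial has 80% power for a 4.2-point difference and about 54% power for the MCID of 3.1 (unadjusted, two-sided 5%). With adjustment for baseline HADS, power at 3.1 is about 66% if the baseline to 6-month correlation is 0.5 (assumed), and at least 80% only if it is about 0.68 or higher.

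If the sponsor can justify a correlation, for example from its phase II data, that value and the resulting power should replace the 0.5 illustration. Section 11.2 should also say that the 5% type I error is two-sided, if that is what was used.

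**Optional.** State that a non-significant result whose 95% CI includes a 3.1-point reduction will be reported as inconclusive.

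**Cost.** Wording only. The stated power becomes less favourable; no extra patients are needed and the analysis does not change.

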11.3 Randomization

The randomization algorithm will be constructed by the study statistician using a permuted blocks scheme with randomly varying block sizes, within strata defined by age group and sites. Randomized assignments will be administered by a research associate using REDCap. Randomization will be stratified by age (patients ages 12-17 versus ages 18-24) and site.

11.4 Analysis Plan

11.4.1 Primary Outcome (Anxiety and Depression [HADS scores]). Our primary outcome is AYA reported total HADS score at 6 months. Because the amount of change depends strongly on the initial score at baseline we will control for baseline score as a covariate in the regression. Regression models will be used to estimate mean-level differences and 95% confidence intervals comparing scores in the PRISM intervention to those in usual care. The total HADS score will be the outcome, and PRISM intervention indicator will be the predictor of interest. Baseline HADS score, age group, site and other unbalanced confounders will be covariates in the regression. With this model specification, the regression coefficient of PRISM indicator captures the difference in the average changes (from baseline to 6 months) for the HADS score between PRISM arm and usual care arm. Thus the primary hypothesis can be tested by applying the Wald t-test to the regression coefficient of PRISM indicator. The same analysis will be undertaken for the domain subscales of anxiety and depression (HADS-A and HADS-D subscale scores).

11.4.2 Secondary Outcomes

11.4.2.1 AYA patient reported outcomes. The same analysis as above will be undertaken for the secondary outcomes of symptom burden, generic- and cancer-specific quality of life, hope, and resilience.

11.4.2.2 Cost per Quality Adjusted Life Year (QALY). We will use a cost-effectiveness framework to evaluate the overall value of PRISM.⁸¹ We anticipate that supportive care and PRISM will be cost-effective compared to supportive care alone. The main cost-analyses will determine the total, per-patient, 6-month costs of PRISM versus usual care. Using Quality-adjusted life years (QALYs) we will then estimate the incremental cost-effectiveness ratio (ICER)

Costs will be calculated with a micro-costing approach, multiplying resource use by unit costs.⁸⁰ Resource utilization will be valued through the Medical Expenditures Panel Survey^{125,126} and the Healthcare cost and utilization project,^{127,128} with additional information from the Federal Supply Schedule.^{78,79} For example, PRISM utilization will be calculated by estimated cost per visit category (e.g., in-person check-in with/without formal session), plus estimated costs of intervention delivery (including facilities and overhead). We will add a fixed \$50 per patient cost for caseload supervision and information support, consistent with prior analyses of collaborative psychosocial interventions.¹²⁹⁻¹³¹ Patient costs will be valued using opportunity cost methods and the proxy-good method in sensitivity analyses.¹³²

We will calculate ICERs to provide information on the incremental cost for each additional unit of change in QALYs. Because the goal of cost-effectiveness analysis is to inform decisions about resource allocation and assess intervention value, traditional hypothesis testing is rarely utilized.⁸⁰ Uncertainty in all ICER estimates will be quantified using non-parametric bootstrapping and calculation of a 95% confidence interval (CI) with Fieller's method.^{133,134} We will calculate QALYs with standard utility values (preference-based measures of quality of life ranging from 0 to 1, defined by the Health Utilities Index).¹⁰² Sensitivity analyses will calculate QALYs with assigned values for HADS scores (1.0 for no, 0.8 for mild, and 0.6 for severe anxiety or depression) as described previously.¹³⁵⁻¹³⁷ The rationale for this dual approach is that preference-based scoring in pediatrics has limitations because rapid developmental changes make it difficult to identify health attributes (and hence, utility values) relevant to all age groups.¹³⁸

11.4.3 Parent Outcomes. The same analysis as above (primary outcome and Aim 2A) will be undertaken for the parent outcomes.

11.4.4 Patient Outcome Trajectories. We will use descriptive statistics to summarize patient-reported outcomes in each study arm at enrollment, 3 months and 6 months. We will plot individual patient trajectories across all time-points for each outcome measure and attempt to identify trajectory patterns (e.g., stable vs. temporary or sustained improvement or deterioration) within study groups. We will also plot outcome summaries across time by study group to assess between-

group differences in overall trajectories and variability.

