
1.2 Purpose of the Study Protocol

The protocol is intended to be used by all study staff as the approved procedures for conduct of the study.

1.3 Primary Aim: Evaluate the effect of PRISM compared to usual care on symptoms of anxiety and depression.

Primary Outcome Measure: AYA-reported mixed affective (anxiety and depression) symptoms 6-months post enrollment (measured with the Hospital Anxiety and Depression Scale).¹

Primary Hypothesis: PRISM will be associated with lower anxiety and depression compared to usual care.

1.4 Secondary Aims:

1.4.1 Evaluate PRISM's impact on other key patient-reported outcomes 6-months following enrollment.

Outcome Measures: (a) Symptom Burden (measured by the Memorial Symptom Assessment Score)²; (b) Health-Related Quality of Life (measured with the Pediatric Quality of Life [PedsQL] 4.0 Generic and 3.0 Cancer Modules)^{3,4}; (c) Hopeful patterns of thought (Hope Scale)⁵; and, (d) resilience (Connor Davidson Resilience Scale, CDRISC-10).^{6,7}

Hypothesis: PRISM will be associated with (a) lower total symptom burden; (b) *higher* quality of life; (c) higher hope; and (d) higher resilience, compared to usual care.

1.4.2 Evaluate the cost-effectiveness of the PRISM intervention.

Outcome Measure: Cost per Quality Adjusted Life Years (QALY)

Expected findings: PRISM will be cost-effective compared to usual care, considering a standard willingness to pay threshold of \$150,000 per QALY gained

Exploratory Outcomes: (i) PRISM's cost utility as a function of treatments related to patient-reported anxiety and depression; and, (ii) PRISM's cost per clinically relevant consequence such as change in mental health score or adherence.

1.4.3 Evaluate the impact of PRISM on parent outcomes 6-months following enrollment.

Outcome Measures: Health-Related Quality of Life (SF-36)⁸; anxiety (Generalized Anxiety Disorder Screener, GAD-7),⁹ and depression (PHQ-8),^{10,11}

Hypothesis: Parents of AYAs who receive PRISM will report higher quality of life and lower psychological distress compared to parents of AYAs in usual care.

Exploratory Outcome: Family Experience (selected items from Hospital Consumer Assessment of Healthcare Providers and Systems [HCAHPS] survey).¹²

1.4.4 Describe individual and group 6-month trajectories for patient reported outcomes of usual care and PRISM participants.

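### The 150,000-dollars-per-QALY question is answered only by an ICER with a Fieller interval, which is likely to be unbounded if the utility effect is small; net monetary benefit should be the prespecified statistic.

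*Combined protocol and SAP*

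**What the plan says.** Section 1.4.2 makes cost per QALY a secondary outcome and gives as the expected finding that "PRISM will be cost-effective compared to usual care, considering a standard willingness to pay threshold of" 150,000 dollars per QALY gained. Section 11.4.2.2 sets the horizon: "The main cost-analyses will determine the total, per-patient, 6-month costs of PRISM versus usual care". QALYs come from the Health Utilities Index (HUI), which section 9.7 schedules at baseline, month 3 and month 6. On uncertainty, section 11.4.2.2 says: "Uncertainty in all ICER estimates will be quantified using non-parametric bootstrapping and calculation of a 95% confidence interval (CI" by Fieller's method. It adds that formal hypothesis tests are uncommon in this kind of analysis.

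Section 11.2 sets the sample size: "Assuming 20% attrition, we will randomize 90 AYAs (45 per arm) to obtain an evaluable sample size of 70 AYA participants (35 per arm"). It gives no precision target for the economic outcomes and relies on confidence intervals to convey precision.

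The plan does not name net monetary benefit, an acceptability curve or a probability of cost-effectiveness at the threshold. It has no rule for reporting an unbounded Fieller set or bootstrap draws that fall in several quadrants. Section 11.4.2.1 extends the baseline-adjusted model to symptom burden, quality of life, hope and resilience. Baseline-HUI adjustment of QALYs is not stated.

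**The concern.** The objective is a threshold question, but the planned summary is a ratio whose denominator may be close to zero. A 95% Fieller set for cost difference over QALY difference is an ordinary interval only if the QALY difference excludes zero at 5%. Otherwise it is the whole real line or two disjoint rays. Bootstrapped ratios have a related difficulty: a negative ratio can mean that PRISM is cheaper and better, or dearer and worse, so the draws have no useful ordering.

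At stake is whether the result for section 1.4.2 can be reported in a form that a reader can set against 150,000 dollars. If it cannot, the summary would have to be chosen after the data are seen.

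**Working it through.** **Sample-size basis.** The plan states no figure for QALY precision, so the nearest stated figure to reproduce is the HADS detectable difference: "This sample size achieves 80% power to detect a 4.2-point increase in the mean 6-month total HADS score". With 35 per arm, SD 6.2 and two-sided 5% (sidedness is not stated, but this reproduces the figure), (1.96 + 0.84) × 6.2 × √(2/35) = 4.15, or 4.21 with the t distribution. The stated 4.2 is confirmed, so 35 per arm is the right basis.

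**Boundedness.** The Fieller set is all R with |ΔC − R·ΔQ| ≤ 1.96 × SE(ΔC − R·ΔQ). Squared, this is a quadratic in R with leading coefficient ΔQ² − 1.96²·SE(ΔQ)². The set is bounded only if that coefficient is positive, that is, |ΔQ|/SE(ΔQ) > 1.96. The chance of a bounded interval therefore equals the power for the QALY difference.

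**QALY standard error.** The HUI SD, the between-visit correlation ρ (taken as equal for all pairs of visits) and the utility gain d are my assumptions, because the documents give none. The trapezoid rule at 0, 3 and 6 months gives weights 0.125, 0.25 and 0.125 years. A gain d present at months 3 and 6 gives ΔQ = 0.375·d.

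- Unadjusted: SE = SD × √(V × 2/35), with V = (1 − ρ) × 0.09375 + ρ × 0.25. At ρ = 0.5, V = 0.1719. With SD 0.20, SE = 0.0198. A bounded interval needs 1.96 × 0.0198 = 0.039 QALY, which is 0.104 in utility.
- Adjusted for baseline HUI: V = 0.078125 × (1 − ρ²) + 0.0625 × (ρ − ρ²). At ρ = 0.5, V = 0.0742 and SE = 0.0130. A bounded interval needs 0.0255 QALY, or 0.068 in utility.

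Chance of a bounded interval (normal approximation):

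| SD | ρ | d = 0.05, unadjusted | d = 0.05, adjusted | d = 0.10, unadjusted | d = 0.10, adjusted |
|---|---|---|---|---|---|
| 0.15 | 0.5 | 24% | 48% | 71% | 97% |
| 0.15 | 0.7 | 21% | 62% | 64% | >99% |
| 0.20 | 0.5 | 16% | 30% | 47% | 82% |
| 0.20 | 0.7 | 14% | 40% | 41% | 93% |
| 0.25 | 0.5 | 12% | 21% | 33% | 63% |
| 0.25 | 0.7 | 11% | 28% | 29% | 78% |

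As a cross-check, I placed the SD directly on 6-month average utility (0.15, 0.20, 0.25) and used the noncentral t. At an average difference of 0.05 this gives 28%, 18% and 13%.

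**Horizon.** With horizon T, ΔQ = T × Δu and SE(ΔQ) = T × SE(Δu), so T cancels. For average-utility SD 0.20 and difference 0.05, power is 18.0% at 0.5, 1 and 2 years alike.

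**Same data, two summaries.** Suppose an observed gain of 0.02 QALY (SE 0.0198) and a saving of 2,000 dollars (SE 1,500), with independent errors; all four figures are assumed. The leading coefficient is 0.02² − 1.96² × 0.0198² = −0.0011 and the discriminant is negative, so the Fieller set is the whole line. Net monetary benefit is 150,000 × 0.02 + 2,000 = 5,000 dollars. Its SE is √((150,000 × 0.0198)² + 1,500²) = 3,327, so the 95% CI is about −1,500 to 11,500. The corresponding probability of cost-effectiveness is about 93%. Both summaries are inconclusive at 5%, but only the second shows direction and size.

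**The case against.** The strongest reply is that Fieller's method already makes the comparison. Setting R = 150,000 in the definition above gives exactly the condition that the parametric confidence interval for net benefit includes zero. So 150,000 lies outside the Fieller set, bounded or not, exactly when net benefit at 150,000 is significant. Simulation (35 per arm, 20,000 runs in each of four assumed scenarios) agreed in every run. With assumed savings of 3,000 or 10,000 dollars, 30% and 52% of unbounded sets still excluded 150,000. This stands. A reader might infer that the planned analysis cannot answer section 1.4.2; that is too strong. The planned bootstrap could also supply net benefit, although the plan does not say that it will.

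A reader might also blame the 6-month horizon. The cancellation of T shows otherwise. A short horizon would matter only if benefit grew later.

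Nor do the documents establish that the interval will usually be unbounded, since the SD and effect are assumed. Consider the plan's HADS-based sensitivity utilities, with assumed cut-offs and correlations of 0.3 to 0.7. A 3.1-point HADS effect then gives a bounded interval in about 20 to 46% of trials unadjusted. With baseline adjustment it is 41 to 85% if the effect is full by month 3, and 21 to 52% if it builds linearly to month 6. For 4.2 points the three ranges are 30 to 70%, 60 to 98% and 32 to 77%.

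It is tempting to extend the point to the cost-consequence ratios in section 11.5.2. That does not follow. They are exploratory, the plan says they are not thresholds, and section 11.5.2 specifies no interval. The HADS ratio also has the powered outcome as its denominator, significant in about 80% of trials at a 4.2-point effect.

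Finally, section 11.2 openly accepts limited economic precision. That is fair, but it does not settle which summary to report.

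**Conclusion.** The point holds as a cheap improvement to one secondary objective, not as an error that invalidates the analysis. The plan poses a question at 150,000 dollars per QALY and prespecifies only a ratio interval, with no rule for when that interval is unbounded. For a utility gain of about 0.05, an unbounded set is the more likely outcome in every unadjusted setting tabulated and in all but one of the adjusted settings. At a gain of 0.10 with baseline adjustment, a bounded interval is the more likely outcome throughout.

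These figures rest on assumed HUI SD, correlation and effect, complete HUI data at three visits and 35 per arm. The boundedness condition and the irrelevance of the horizon do not depend on the assumed values. Net monetary benefit adds no power at 150,000; its advantage is an estimate that is finite, directional and on the scale of the stated threshold.

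**What to change.** In section 11.4.2.2:

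- Make incremental net monetary benefit, 150,000 × ΔQALY − Δcost, with its bootstrap 95% CI, the statistic for objective 1.4.2.
- From the same draws, report the cost-effectiveness plane and the probability that PRISM is cost-effective at 150,000 dollars and over a range of thresholds.
- Report the ICER as a point estimate, with a Fieller interval only when the QALY difference excludes zero.
- Adjust QALYs for the baseline HUI. In the SD 0.20, ρ = 0.5 case this cuts the SE from 0.0198 to 0.0130.

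Section 11.5.2 needs no change on this account.

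The cost is SAP wording; data, bootstrap and threshold are unchanged. There are two downsides. Net benefit in dollars is less familiar to clinical readers than a ratio. It will also still be imprecise: with average-utility SD 0.20, the 95% half-width is about 7,200, 11,900 or 48,200 dollars for an assumed cost SD of 2,000, 20,000 or 100,000.
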